A relatively novel technology, the automated fundus related perimetry technology (also known as microperimetry-MP), constitutes a surplus tool to assess retinal function, in this case sensitivity, with the advantage of precisely correlating the retinal sensitivity to the anatomical changes seen in scanning laser ophthalmoscope (SLO) images and autofluorescence images. In the last 5 years, many studies using MP have reported cross-sectional findings of retinal sensitivity impairment in STGD [22-25]. The majority of these findings were based on the evaluation of microperimetric mesopic response (cones and rods response combined) without any consideration to differential activity and impairment of the two types of photoreceptors during the natural course of the disease.

More recently, Crossland and colleagues followed by Birch and colleagues have described and validated protocols to measure rod sensitivity using a modified MP-1 [26, 27], which may allow, for the first time, the precise evaluation of rod function and its correlation with morphologic damage in the natural history of STGD.

Ultimately, the understanding of the differential impairment of the cone and rods photoreceptors, through microperimetry findings, may establish consistent and reliable parameters to monitor patients and investigate potential treatments for STGD, which thus far, has not been available for patients with ABCA4-related retinal disease.

2. Objectives (include all primary and secondary objectives)

Through a multicenter prospective cohort study on the natural history of STGD (the ProgStar Study), this ancillary study has the main objective of investigating the rod photoreceptors' sensitivity during the natural course of the disease.

The primary objective is:

- To assess the yearly rate of progression of STGD using macular sensitivity under scotopic testing conditions.

The secondary objectives are:

- To correlate scotopic microperimetric changes with anatomical status/progression as determined by visual acuity, ERG, optical coherence tomography (OCT) and autofluorescence images.
- To determine the variability of the test.
- To determine the earliest functional deficits in STGD
- To establish the best microperimetric parameters to monitor patients with STGD.

3. Background (briefly describe pre-clinical and clinical data, current experience with procedures, drug or device, and any other relevant information to justify the research)

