The study will collect data every 6 months over a 24 months period. Therefore, 5 visits will take place during the study (baseline, months 6, 12, 18 and 24). If enrollment and prospective evaluation of an eligible patient in the ProgStar-02 study started significantly earlier than the start of the SMART study, then it is possible that only 18 months of follow-up will be available. The last ProgStar-02 visit should also be the last SMART study visit. Each visit, all patients will undergo microperimetric examination under scotopic condition in addition to the standard of care procedures included in the ProgStar Study protocol, which are described below:

- best-corrected visual acuity,
- complete ophthalmic exam (including dilated fundoscopy),
- autofluorescence imaging,
- MP and
- spectral-domain optical coherence tomography (SD-OCT) will be performed).

The ProgStar study results will be sent by the participating centers to the Dana Center for of Preventative Ophthalmology of the Wilmer Eye Institute, the Johns Hopkins University, Baltimore, for evaluation, with exception of the results of MP, autofluorescence and optical coherence tomography, which will be sent to a central reading center at the Doheny Eye Institute, Los Angeles, California.

This is a natural history study. There will be no treatments being investigated in this trial.

- b. Blinding, including justification for blinding or not blinding the trial, if applicable. N/A
- c. Justification of why participants will not receive routine care or will have current therapy stopped. N/A
- d. Justification for inclusion of a placebo or non-treatment group. N/A
- e. Definition of treatment failure or participant removal criteria. N/A
- f. Description of what happens to participants receiving therapy when study ends or if a participant's participation in the study ends prematurely. N/A

5. Inclusion/Exclusion Criteria

Inclusion criteria:

- A mandatory inclusion criteria for the index ancillary study is being a participant of the IRB approved ProgStar Study (JHU IRB NA# 00081134). In the ProgStar Study, the study participants are required to meet the following inclusion criteria:
 1. Provide a signed informed consent form and authorization allowing the disclosure and use of protected health information.

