Estimating the yearly growth in the area of the atrophic lesion as measured by fundus auto-fluorescence:

First exploratory analysis looking at the baseline, six, and twelve months overall distribution of the outcome will be performed, outliers and inconsistent measures will be identified and reviewed. Let Y_{iv} represent the area (or a transformation to achieve normality; e.g. square root) of the i th individual at visit v for $v=0, 1, 2, 3, 4$ for the baseline, 6 months, 12 months, 18 months and 24 months visits, respectively. In order to determine the average rate of progression in the population, an appropriate approach will be to allow for each individual to have his/her own intercept and slope and to average them to achieve the overall rate of decline. This is accomplished with a random coefficients regression model of the form:

$$Y_{iv} = (\mu + a_i) + (\Delta + b_i)v + \gamma Z_{iv} + e_{iv}; \text{ where } a_i \sim N(0, \sigma_1^2), b_i \sim N(0, \sigma_2^2), \text{ cov}(a_i, b_i) = \sigma_{12} \text{ and } e_{iv} \sim N(0, \sigma^2).$$

The a_i and b_i are the random departures of the line for the i th individual from the population line with intercept μ and slope Δ . The e_{iv} are the within individual departures from the line of the repeated measurements taken on the i th individual at times 0, 6, 12, 18 and 24 months. Z_{iv} represents a vector of factors that could be related to progression such as age and use of vitamin A supplementation.

The estimate of Δ and its standard error will provide the six-month progression of the lesions. In addition, to explore whether progression may be different for different initial levels, we will carry out the analysis in strata of baseline severity.

A similar approach to will be used to examine progression overtime for the secondary outcomes: retinal thinning, loss of photoreceptors, loss of retinal sensitivity, and changes of BCVA.

Scatterplots with lowess smooth average curves will be used to explore the relationship between variables. A linear mixed model will be then used to analyze and quantify the association between the different variables.

Baseline demographic characteristics are: date of birth, age, sex, and race. Randomization is not applicable.

Data Set Descriptions

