3.7 Schedule of Data Collection

Screening and baseline visits may be combined into one visit if the inclusion criteria are fulfilled and the exclusion criteria do not apply. Follow-up visits will be approximately 6, 12, 18, and 24 months after baseline visit. For these follow-up visits, a time window of \pm five (5) weeks around the calculated, expected date of the follow-up visit is acceptable for the data to be included for that time point.

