7.2. Statistical Analyses

Estimating **the yearly growth in the area of the atrophic lesion** as measured by fundus auto-fluorescence:

First exploratory analysis looking at the baseline, six, and twelve months overall distribution of the outcome will be performed, outliers and inconsistent measures will be identified and reviewed. Let Y_{iv} represent the area (or a transformation to achieve normality; e.g. square

root) of the i^{th} individual at visit v for $v=0, 1, 2, 3, 4$ for the baseline, 6 months, 12 months, 18 months and 24 months visits, respectively. In order to determine the average rate of progression in the population, an appropriate approach will be to allow for each individual to have his/her own intercept and slope and to average them to achieve the overall rate of decline. This is accomplished with a random coefficients regression model of the form:

$$Y_{iv} = (\mu + a_i) + (\Delta + b_i)v + \gamma Z_{iv} + e_{iv}; \text{ where } a_i \sim N(0, \sigma_1^2), b_i \sim N(0, \sigma_2^2), \text{ cov}(a_i, b_i) = \sigma_{12} \text{ and } e_{iv} \sim N(0, \sigma^2).$$

The a_i and b_i are the random departures of the line for the i^{th} individual from the population line with intercept μ and slope Δ . The e_{iv} are the within individual departures from the line of the repeated measurements taken on the i^{th} individual at times 0, 6, 12, 18 and 24 months. Z_{iv} represents a vector of factors that could to be related to progression such as age and use of vitamin A supplementation.

The estimate of Δ and its standard error will provide the six month progression of the lesions. In addition, to explore whether progression may be different for different initial levels, we will carry out the analysis in strata of baseline severity.

A similar approach to will be used to examine progression overtime for the secondary outcomes: retinal thinning, loss of photoreceptors, loss of retinal sensitivity, and changes of BCVA.

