7.2. Statistical Analyses

Estimating **the yearly growth in the area of the atrophic lesion** as measured by fundus auto-fluorescence:

First exploratory analysis looking at the overall distribution of the outcome at all visits will be carried out, outliers and inconsistent measures will be identified and reviewed. By design, the interval between visits will be variable. For each individual, a slope will be estimated using the available data points by fitting a regression line to the data points. For example, if the i^{th} subject contributes with 3 visits the times $t_{i0}, t_{i,-1}, t_{i,-2}$ with outcome observations $y_{i0}, y_{i,-1}, y_{i,-2}$ will be used to estimate the slope b_i , which will be obtained from the regression $y_{ik}=a+b_i t_{ik}$. ($k=0,-1,-2$). Once the data from each individual has been used to estimate the slope (b), the second stage of the analysis will be to explore which exposures/risk factors determine the heterogeneity of the slopes. Using the slope as the outcome, multivariate regression models will be constructed to identify factors correlating

with progression. Specifically, the correlation to progression of age, severity at first visit, and use of vitamin A supplementation will be examined.

A similar approach to will be used to examine progression over time for the secondary outcomes: retinal thinning, loss of photoreceptors, loss of retinal sensitivity, and changes of BCVA.

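### The prospective and SMART progression model uses visit number as its clock although follow-ups may fall up to five weeks off schedule, and the SAP does not say whether time is actual or scheduled

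*Protocol*

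**What the plan says.** **Model.** SMART eForm A 7.c (Statistical Analyses) defines the outcome "at visit v for $v=0, 1, 2, 3, 4$ for the baseline, 6 months, 12 months, 18 months and 24 months visits" and multiplies the slope by v. The residuals are described as departures for repeated measurements taken on each "individual at times 0, 6, 12, 18 and 24 months". The slope is read per visit step: "its standard error will provide the six-month progression of the lesions". PROGSTAR-02 7.2 has the same model and the same reading: "The estimate of Δ and its standard error will provide the six month progression of the lesions".

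**Objective.** The SMART primary objective is annual: "To assess the yearly rate of progression of STGD using macular sensitivity under scotopic testing conditions".

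**Visit timing.** PROGSTAR-02 3.7 allows plus or minus five "weeks around the calculated, expected date of the follow-up visit is acceptable for the data to be included for that time point". The SMART eForm gives no window of its own, and its tests are done at ProgStar visits. Section 3.7.1.2 lets one follow-up's examinations fall on different days provided the window is kept. Section 3.7.2.3 requires the visit date to be documented.

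**Late starters.** For patients who began ProgStar-02 well before SMART, section 4.a of the eForm says "it is possible that only 18 months of follow-up will be available". It adds that the two studies should share their last visit.

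**Retrospective study.** PROGSTAR-01 7.2 takes the other route. It notes "By design, the interval between visits will be variable" and regresses on each person's own visit times.

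**SAP.** The SAP lists all three studies in its title block. It specifies a mixed model with a random coefficient for time and a rate per year, for the prospective and the retrospective cohort. It does not say how time is computed.

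**The concern.** The quantity to be estimated is change per unit of time, and the protocol model measures change per visit. The two agree only if visits keep to schedule on average. When follow-ups run late as a group, more real time, and so more real change, is packed into each visit step, and the slope is overstated. When they run early it is understated. Unlike sampling error, this does not shrink with more participants.

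Individual slopes are exposed even when the cohort average is not, because a single person's timing errors need not cancel. That matters for the random-slope variance and for the analyses of which baseline factors go with faster change.

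The study is meant to guide the choice of outcome measures for later trials, so its rates will be reused. The information needed to avoid the problem is largely collected already.

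**Working it through.** **Inputs.** Visit index 0 to 4 and nominal months (SMART 7.c, PROGSTAR-02 7.2); window of ±5 weeks (PROGSTAR-02 3.7). Assumption: six months = 26 weeks. The documents state no figure for the effect of visit timing, so there is none to reproduce. The section's one design figure, N = 170, is not in dispute: (0.9 × (1.960 + 0.842)/0.2)² = 158.9, and dividing by the Wilcoxon efficiency 3/π gives 166.4, within 3% of 170.

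**Formula.** Let visit v take place at week 26v + d(v). Follow-up dates are calculated from baseline, so d(0) = 0. For a straight-line course, the least-squares slope on v relative to the true slope is

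1 + Σ(v − v̄)d(v) / (26 × Σ(v − v̄)²).

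For five visits v̄ = 2 and Σ(v − v̄)² = 10, so the denominator is 260.

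| Pattern d(0..4), weeks | Σ(v − 2)d(v) | Error in slope |
|---|---|---|
| 0, 2.5, 2.5, 2.5, 2.5 | 5 | +1.9% |
| 0, 5, 5, 5, 5 | −5 + 0 + 5 + 10 = 10 | +3.8% |
| 0, 1.25, 2.5, 3.75, 5 | −1.25 + 0 + 3.75 + 10 = 12.5 | +4.8% |
| 0, −5, any, 5, 5 (worst case) | 5 + 0 + 5 + 10 = 20 | +7.7% |

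Reversing the signs gives the same errors downward.

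**Shorter series.** A rate from the first three visits alone, all follow-ups five weeks late, is out by 5/52 = 9.6%. A person with only the six-month follow-up, five weeks late, is out by 5/26 = 19.2%. The first bears on the 12-month endpoint and interim analysis if they use those visits alone. The second concerns one person, not the cohort.

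**Drift that averages zero.** The error is linear in d(v). If each d(v) averages zero and is unrelated to the person's slope, the average error is zero.

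**Simulation.** Random intercept and slope model, N = 70, 100 runs, true slope −1 unit per year. Intercept SD 3, slope SD 0.8 and residual SD 1 are assumptions, because the documents give no scotopic values.

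- Uniform drift within ±5 weeks: −0.997 by visit number, −0.996 by actual time; standard errors 0.1212 and 0.1210.
- All follow-ups five weeks late: visit-number slope steeper by 0.040, matching the 3.8%.
- Half of participants starting SMART late, no drift: difference 0.000, whether v restarts at 0 or keeps the ProgStar-02 numbering.
- Half starting late, all ProgStar-02 follow-ups five weeks late: steeper by 0.022.

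**Late starters in the formula.** Four visits give v̄ = 1.5 and a denominator of 26 × 5 = 130. If the first SMART visit is the ProgStar-02 month-6 visit, it is itself a windowed visit, so d(0) need not be 0. With all four visits equally late, 5 × Σ(v − 1.5) = 0 and the error is 0%. The worst pattern for one person, −5, −5, 5, 5, gives 20/130 = 15.4%.

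**The case against.** The strongest reply is that the SAP has moved on. It drops visit number, models time, reports a rate per year and names the same model for the retrospective cohort, where visit number could not serve as a clock. Elapsed years is therefore the natural reading. That carries weight, but scheduled time coded 0, 0.5, 1.0 also yields a rate per year, and the only text that defines the time axis for the prospective studies is nominal. The ambiguity stands.

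Second, the window is symmetric and nothing in the documents shows systematic lateness. This also stands: 3.8% is conditional, and 7.7% is an extreme for one person, not an expected cohort bias.

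Third, reading the slope as six-month progression is openly stated, and doubling it gives a yearly figure. True; the unit is not the defect, the nominal clock is.

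Two stronger readings are tempting, and the documents support neither. A reader might infer that starting SMART at a later ProgStar-02 visit mis-scales the rate. It does not: visits stay about six months apart, so only the origin of v moves and some precision is lost. A reader might also infer that scotopic tests will be matched by SMART visit number to images taken six months earlier. No section prescribes such pairing, and section 4.a has scotopic testing done at the same visits as the ProgStar procedures. The absence of a linking rule is worth closing, but it is not a stated error.

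Examinations on different days add nothing beyond the window at follow-up, since section 3.7.1.2 keeps them inside it.

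**Conclusion.** The point holds as a modest weakness in how time is defined. The prospective and SMART protocol text uses nominal visit number, visits may be off by up to five weeks, and the SAP does not settle which clock applies. Over five visits the population rate is overstated by 3.8% if every follow-up is five weeks late (understated by as much if all are five weeks early), and one person's slope can be wrong by up to 7.7%. It is unbiased if drift averages zero and is unrelated to progression.

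These figures rest on 26-week half-years, a straight-line course and an on-schedule baseline. They are percentages of whatever the true rate is; with no scotopic rate or SD in the documents, they cannot be turned into sensitivity units or set against the precision expected from up to 70 participants. The existing results are not shown to be wrong. A better definition is available at almost no cost, and PROGSTAR-01 already uses it.

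**What to change.** In SMART 7.c, PROGSTAR-02 7.2 and the SAP, replace v by t, the actual elapsed time in years from recorded examination dates. Count t from one baseline date per participant within each study: the SMART baseline for SMART, the ProgStar-02 baseline for PROGSTAR-02. A single origin per study avoids giving each modality its own clock. The slope is then the yearly rate directly, and the sentences that describe it as six-month progression should be changed to match.

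For structure-function analyses, state that each scotopic test is linked to the autofluorescence, OCT and acuity data of the same ProgStar-02 visit.

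Cost: a one-line change to the model definition and one sentence on linkage. No new visits or tests are needed and no precision is lost. Visit dates are already documented; where one visit's examinations were split over days, the date of each examination should be carried into the analysis file.

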Name of Sponsor:	Foundation Fighting Blindness Clinical Research Institute	Protocol #: CRI-PROGSTAR-02 IND#: N/A
Name of Product:	N/A	
Protocol Title:	The Natural History of the Progression of Atrophy Secondary to Stargardt Disease (STGD): A Prospective Longitudinal Observational Study	
Clinical Phase:	N/A – Natural History Study	
Treatment Indication:	N/A	
Objectives:	
The primary objective is:
 
 • To assess the yearly rate of progression of STGD using the growth of atrophic lesions as measured by fundus autofluorescence (FAF) imaging. 
The secondary objectives are:
 
 • To assess the yearly rate of progression of STGD using the rate of retinal thinning and the rate of loss of photoreceptors as measured by spectral-domain optical coherence tomography (sd-OCT) • To assess the yearly rate of loss of retinal sensitivity as measured by microperimetry • To assess the yearly rate of visual acuity changes using the Early Treatment Diabetic Retinopathy Study (ETDRS) visual acuity protocol • To correlate the presence and progression of morphological abnormalities in FAF and sd-OCT images with visual function as measured by microperimetry and visual acuity. • To perform exploratory analysis that examines factors associated with effects on STGD progression, such as the use of vitamin A supplementation and mutations in the ABCA4 gene 	
Study Design:	Prospective longitudinal observational study over a period of 24 months.	

Name of Sponsor:	Foundation Fighting Blindness Clinical Research Institute	Protocol #: CRI-PROGSTAR-02 IND#: N/A
Name of Product:	N/A	
Participant Population:	Up to a total of 250 (minimum of 150) patients, including males and females age 6 years and older affected by STGD that have an atrophic lesion in at least one eye with a minimum diameter of at least 300 microns, and a sum of all lesions less than or equal to 12 mm ² (five disc areas).	
Test Product, Dose, Mode of Administration:	N/A	
Outcome Variables	
 • Growth of atrophic lesions as measured by FAF imaging performed at 12 and 24 months. • Rate of retinal thinning and photoreceptor loss as measured by sd-OCT at 12 and 24 months. • Loss of retinal sensitivity as measured by microperimetry at 12 and 24 months. • Change of best-corrected visual acuity by using the ETDRS protocol at 12 and 24 months. 	

Research - A systematic investigation, including the development, testing and evaluation of an idea, designed to develop or contribute to generalizable knowledge. Activities that meet this definition constitute research whether or not they are conducted or supported under a program that is considered research for other purposes. For example, some demonstration and service programs may include research activities.

Clinical Investigation - Any experiment in which a drug or therapy is administered, dispensed, or used for treating one or more human participant. This definition applies to research involving the use of FDA-regulated products. Even if a clinical investigation does not meet the definition of research, it is participant to the same regulations as research.

Human Participant - A living individual about whom an investigator is conducting research, obtains data, through intervention or interaction with the individual, or identifiable private information.

Human Anatomical Substances - Any human organs, tissues, cells, or body fluids including but not limited to blood/sera (finger stick, ear stick, venipuncture, etc.), hair, nails, teeth, skin, sputum or cells gathered from mouth washing, nasal or oral swabs, placenta or amniotic fluid.

Individually Identifiable Private Information - *Private information* includes information about behavior that occurs in a context in which an individual can reasonably expect that no observation or recording is taking place. This information has been provided for specific purposes by an individual and the individual can reasonably expect that private information will not be made public (for example, a medical record). *Individually identifiable* means that the identity of the participant is known or that their identity may readily be ascertained by the investigator or that their identity is associated with the information.

Protected Health Information (PHI) - Any individually identifiable health information held by a covered entity, as defined in the Health Insurance Portability and Accountability Act (HIPAA).

Covered Entity - An organization engaged in the treatment of patients, responsible for obtaining payment for such treatment, or engaged in other healthcare operations where PHI is electronically exchanged.

Authorization - Written permission from an individual allowing a Covered Entity to use or disclose specified PHI for a particular purpose (such as research).

Minimal Risk - The probability and magnitude of harm or discomfort in the research are not anticipated to be greater in and of themselves than those ordinarily encountered in daily life, or during the performance of routine physical and psychological examinations or tests.

Legally Authorized Representative (LAR) - An individual or judicial or other body authorized under applicable law to consent on behalf of a potential participant to the participant's participation in the procedure(s) involved in the research. NOTE: State law defines who may act as an LAR. The Institutional Review Board (IRB) of record should be consulted for guidance regarding who can serve as an LAR for research at the research site.

USAMRMC Supported Research - For the purpose of this document USAMRMC supported research includes but is not limited to: (1) Research funded (through grant, contract, cooperative agreement, military interdepartmental purchase request, etc.) by the USAMRMC and (2) Research managed (technical management and/or funds management) by the USAMRMC as directed by Congress (e.g., Telemedicine and Advanced Technology Research Center (TATRC)).

Institutional Review Board (IRB) of Record - The IRB listed on an Institution's Assurance of Compliance that assumes responsibility for review and oversight of a research protocol on behalf of the institution. An IRB of record from each institution engaged in the research must review and approve the protocol; therefore, there can be more than one IRB of record for a protocol. An IRB Authorization Agreement between two IRBs of Record allows one IRB of record to defer to another.

Research Proposal - A research plan submitted to the DOD funding agency in response to a solicitation. The proposal provides an overview of all proposed work to be performed and provides the rationale explaining why the institution should be awarded funds to complete the work. A proposal may consist of multiple research projects conducted under separate protocols at one or more institutions.

Research Protocol - A comprehensive, detailed, and specific plan of action for the execution of research on human participants

Award - A financial agreement such as a grant, contract, or cooperative agreement between the Federal Government and an institution.

Scientific Review – An independent, documented review that objectively evaluates the scientific merit of a research proposal or protocol. Refer to the HRPO Policies and Procedures document on the HRPO website for additional information on scientific reviews.

Contract Officer (CO) – A federal government employee authorized to negotiate awards and commit funds on behalf of the U.S. Government.

Contract Specialist - A federal government employee assigned to assist the CO with award related issues. The contract specialist is the primary point of contract for award related issues.

Contract Officer's Representative (COR) - A federal government employee assigned by the CO to manage the technical aspects and performance of an award on behalf of the DOD program office responsible for oversight of the research. The COR may serve as the **Grant Manager or Project Manager** or may have assistance from other personnel within the DOD program office in executing COR responsibilities.

Human Subjects Protection Scientist (HSPS) - A federal government employee or contractor within the HRPO responsible for assisting investigators with the HRPO review and approval process. The HSPS is the investigator's primary point of contact for questions regarding the human research review process and other issues related to human subjects protection.

Army Human Research Protection Office (AHRPO) - The office that reports to the Assistant Surgeon General, Force Projection and is responsible for human research policy, education, and oversight for the U S Army. The AHRPO administers DOD Assurances of Compliance.

Informed Consent - Informed consent is an ongoing process that provides the participant, or legally authorized representative (LAR), with sufficient details about a study so that he/she can make a voluntary decision about participation. Often a written consent form is employed to facilitate initial discussion of a study, and includes descriptions of study procedures, potential risks and benefits, and other pertinent information. Informed consent is an ongoing, interactive process and the participant's voluntary decision about continuing to take part in the trial should be reassessed throughout the study.

Enrollment - To register, enter, screen, randomize, or otherwise formally initiate a participant's participation in a study. Informed consent precedes enrollment. The number of participant consented may differ from the number of participants enrolled in a study (e.g., a participant may give consent to participate in a study but may be determined to be ineligible upon screening; commonly called a "screen failure").

Screening - A process of actively assessing a potential participant for inclusion in a study based on compatibility with pre-determined inclusion/exclusion criteria, ability and willingness to complete the study, and other factors. Screening that does not access, collect, or record a participant's protected health information may take place before informed consent is obtained. However, informed consent must be obtained prior to screening procedures that use protected health information or involve procedures that a participant would not normally undergo.

1 Introduction

Stargardt disease (STGD1; OMIM: 248200), initially described by the German ophthalmologist Karl Stargardt in 1909, is predominantly an autosomal recessively inherited disorder, although an autosomal dominant Stargardt-like phenotype has also been described [1]. Stargardt disease is the most common form of juvenile macular degeneration with an estimated incidence of 10 – 12.5 per 100,000 and about 95% of cases are caused by mutations in the *ABCA4* gene [2, 6] that lead to an autosomal recessive inherited disorder, although an autosomal dominant Stargardt-like phenotype [3] has also been described associated with mutations in the *ELOVL4* and *PROM1* genes [4, 5].

Patients with STGD develop a progressive impairment of visual acuity, which begins most frequently within the first or second decades of life [7]. However some patients do not lose visual acuity until the fourth or even fifth decade of life. The loss of acuity is accompanied by atrophic-appearing lesions within the macula and the presence of yellow-white lesions about the retinal pigment epithelium (RPE), which are referred to as “fundus flecks”. The fundus changes apparent clinically are caused by excess accumulation of lipofuscin in the RPE (Figure 1). RPE lipofuscin is a heterogeneous material composed of a mixture of lipids, proteins, and different fluorescent compounds [8]. The natural autofluorescent properties of lipofuscin have led to the use of confocal scanning laser ophthalmoscopy (cSLO), and autofluorescence (AF) imaging, as convenient, noninvasive methods for determining the distribution of lipofuscin in human participants. [9-11].

Figure 1:

[figure not shown]

Figure 1: AF images of both eyes of a patient with bilateral central atrophy of the RPE. Stars: fixation loci determined individually in each eye. The contrast of each grayscale image is uniformly stretched for better visibility of features [12].

